### **History of Changes**

Version Date	Description
Version 1.0—21NOVEMBER2019	Original Document
Version 2.0 – 5 NOVEMBER 2021	Protocol Revision

## LIST OF ABBREVIATIONS

ADAPT	A Direct Aspiration First Pass Technique
ADE	Adverse Device Effect
AE	Adverse Event
AIS	Acute Ischemic Stroke
ASPECTS	Alberta Stroke program early CT score
BA	Basilar Artery
CEC	Clinical Events Committee
CT	Computed Tomography
EC	Ethics Committee
eCRF	Electronic Case Report Form
EDC	Electronic Data Capture
GCP	Good Clinical Practice
HIPAA	Health Insurance Portability and Accountability Act
ICA	Internal Carotid Artery
ICF	Informed Consent Form
ICH	International Council for Harmonization
IFU	Instructions for Use
IV	Intravenous
IV t-PA	Intravenous tissue Plasminogen Activator
LVO	Large Vessel Occlusion
MCA	Middle Cerebral Artery
mITT	Modified Intent-to-Treat
MRI	Magnetic Resonance Imaging
mRS	Modified Rankin Scale
mTICI	modified Thrombolysis in Cerebrovascular Infarction
NIHSS	National Institutes of Health Stroke Scale
PHI	Protected Health Information
PP	Per Protocol
PI	Principal Investigator
PMCF	Post-Market Clinical Follow-Up
RBC	Red Blood Cell
SADE	Serious Adverse Device Effect
SAE	Serious Adverse Event
SAP	Statistical Analysis Plan
SAS	Statistical Analysis Software
SDV	Source Data Verification
SOC	Standard of Care
SOP	Standard Operating Procedure
US	United States
USADE	Unanticipated Serious Adverse Device Effect
VA	Vertebral Artery
WBC	White Blood Cell

## PROTOCOL SUMMARY

Title of Study	Prospective Evaluation to Characterize the Real-World Performance of the EMBOVAC™ Aspiration Catheter for Neurothrombectomy: A Post-Market Clinical Follow-up Trial.	
Short Title	PERFECT	
Study Sponsor	CERENOVUS [name]	
Study Device	EMBOVAC™ Aspiration Catheter	
Indication	The EMBOVAC™ Aspiration Catheter is indicated for general intravascular use in the neuro vasculature. The catheter can be used to facilitate introduction of diagnostic or therapeutic agents and is also intended for use in removal/aspiration of emboli and thrombi from selected blood vessels in the neuro vasculature.	
Study Design	Prospective, multi-center, single arm, post-market clinical follow-up study.	
Sample Size	Approximately 100 subjects will be enrolled.	
Number of Sites	Approximately 10 institutions primarily in Europe.	
Study Duration	Start Date: 2020	End Date: 2022
Study Procedures	
EMBOVAC™ Aspiration Catheter is used with ADAPT (A Direct Aspiration, First Pass Technique) as the first attempted device/technique for mechanical thrombectomy in the subject.
 
The study evaluation time points follow the site's standard of care and include:
 
 
1. Study Procedure
 
2. 24 Hour follow-up (+/- 12 hrs)
 
3. 7 Day / Discharge follow-up (-1/+7 days) (whichever comes first)
 
4. 90 Day Follow-up (+/- 14 days)
 
	
Primary Objective	The primary objective of this Post-Market Clinical Follow-Up (PMCF) study is to characterize the performance of the EMBOVAC™ Aspiration Catheter in the treatment of acute ischemic stroke in a real-world clinical setting.	

Secondary Objective	The secondary objective is to confirm the benefit of a 'system approach' using Cerenovus products (e.g., distal access catheter, balloon guide catheter) which have been designed for use together in the treatment of acute ischemic stroke.
Primary Endpoint	Proportion of patients having successful revascularization, defined as number of subjects achieving a modified Thrombolysis in Cerebral Infarction (mTICI) score of $\geq 2b$ at the end of the procedure, as determined by Core Lab.
Secondary Effectiveness Endpoints	
 
✓ Successful Revascularization (final mTICI <math>\geq 2b</math>) without rescue therapy, as determined by Core Lab
 
✓ Complete Revascularization (final mTICI <math>\geq 2c</math>), as determined by Core Lab
 
✓ First Pass Effect (mTICI <math>\geq 2c</math> without rescue), as determined by Core Lab
 
✓ Modified First Pass Effect (mTICI <math>\geq 2b</math>), as determined by Core Lab
 
✓ Time to recanalization (Time from arterial puncture to complete recanalization mTICI <math>\geq 2b</math>), as determined by Core Lab
 
✓ Modified Rankin Scale 0-2 at 90 Days
 

Secondary Safety Endpoints	
 
✓ Devices related serious adverse events within 90 days
 
✓ sICH at 24h post procedure specified according to the Heidelberg Bleeding Classification (HBC)
 
✓ NIHSS at 24h post procedure
 
✓ 90 Day All-Cause Mortality
 

Health Economic Endpoints	
 
✓ Hospitalization length of stay for index procedure and unscheduled re-hospitalizations
 
✓ Healthcare resource utilization for index procedure, post-procedure and re-hospitalizations for unscheduled events
 

Inclusion Criteria	
 
1. Subject <math>\geq 18</math> years old.
 
2. Subject experiencing acute ischemic stroke with angiographic confirmation of Large Vessel Occlusion (LVO) of the distal
 

	
intracranial internal carotid artery, middle cerebral artery (M1 or M2) or anterior cerebral artery (A1 or A2).
 
 
3. A clinical decision has been made to use the EMBOVACT™ aspiration catheter prior to enrollment in the research.
 
4. EMBOVAC™ Aspiration Catheter is attempted to be used for the first 3 clot removal passes for the target intracranial occlusion (if 3 passes are needed) using A Direct Aspiration, First Pass Technique (ADAPT). Exception: it is not considered rescue therapy if use of another device is needed to remove distal occlusion in a vessel smaller than 2 mm after the first pass.
 
5. Pre-stroke mRS <math>\leq 1</math>
 
6. NIHSS <math>\leq 30</math>
 
7. Informed Consent has been provided by the subject or the subject's legally authorized representative.
 

Exclusion Criteria	
 
1. Potential study candidate has already undergone standard of care assessments or treatment that deviate from the clinical research protocol requirements (e.g., 24 hour imaging conducted outside the protocol specified window).
 
2. All patients with severe hypertension on presentation (SBP <math>> 220</math> mmHg and/or DBP <math>> 120</math> mm Hg). All patients, in whom intravenous therapy with blood pressure medications is indicated, with hypertension that remains severe and sustained despite intravenous antihypertensive therapy (SBP <math>> 185</math> mmHg and/ or DBP <math>> 110</math> mmHg).
 
3. Known cerebral vasculitis.
 
4. Known cancer with life expectancy less than 12 months.
 
5. Stenosis, or any occlusion, in a vessel proximal to the target occlusion that requires treatment or prevents access to the site of occlusion.
 
6. Computed tomography (CT) or Magnetic Resonance Imaging (MRI) evidence of recent/ fresh hemorrhage on presentation.
 
7. Baseline computed tomography (CT) or MRI showing mass effect or intracranial tumor (except small meningioma).
 
8. Evidence of dissection in the extra or intracranial cerebral arteries.
 
9. Occlusions in multiple vessels.
 
10. Confirmation of positive pregnancy test according to site specific standard of care (e.g. test, verbal communication).
 
11. Currently participating in an investigational (drug, device, etc.) clinical trial that may confound study endpoints. Patients in observational, natural history, and/or epidemiological studies not involving intervention are eligible.
 

Sample Size Justification	
There is no statistical power calculation and no hypothesis testing for this post-market study. 100 subjects are deemed sufficient to characterize the performance of EMBOVAC™ Aspiration Catheter.
 
Approximately 100 subjects will be enrolled. With an enrolled sample size of 100 and an attrition rate of no more than 5%, the precision (margin of error) for the primary endpoint is anticipated to be around 8.0% based on 2-sided 95% confidence intervals, where the primary endpoint rate is estimated to be 80%.
 $\text{Margin of error} \approx 1.96 \times SE = 1.96 \times \sqrt{\frac{p(1-p)}{n}} =$ $= 1.96 \times \sqrt{\frac{0.8 \times (1-0.8)}{95}} = 8.0\%$ 
where SE denotes the standard error and <math>p</math> denotes the proportion of subjects who achieve the primary endpoint.

Statistical Analysis	
Demographics, baseline subject characteristics, procedure characteristics and the primary and secondary endpoints will be presented for each analysis population.
 
Descriptive summary statistics will be presented for all endpoints. The number and percentage of subjects will be summarized for categorical variables. Descriptive statistics for continuous variables will include the number of subjects, mean, standard deviation, median, minimum and maximum.

Interim Analysis	
Interim analyses will be conducted for regional (outside Europe, as well as for European MDR) regulatory submission purposes. Only descriptive statistics will be reported. Results of the interim analyses will not be used as a basis for stopping the trial early.

Laboratories	
Imaging Core Lab      Clot analysis lab   

## SCHEDULE OF ASSESSMENTS

**Table 1 Schedule of Assessments**

Assessments	Enrollment				Follow-up	
	Baseline	Procedure	24hrs post-procedure (+/- 12 hrs)	7 days/ discharge (- 1/+7 days) (whichever comes first)	📞 90 Day Follow-up (+/- 14 days)	Unscheduled (6)
Eligibility Screening	X	X	X	X		
Informed Consent	Patient consent may be obtained up to 45 days post procedure					
Demographics and Medical History	X					
IV t-PA administration	O					
Imaging 	X		X			O
NIH Stroke Scale (NIHSS)	X 		X 	O	O	O
Modified Rankin Scale (mRS)	X 			O	X 	O
Angiography 		X				
Review of Reportable AEs 		X	X	X	X	X
Clot Collection 		X				
Health Economics Data Collection		X	X	X	X	X

(1) Imaging will be sent to independent Imaging Core Lab for review

(2) Procedural angiography will be sent to Imaging Core Lab for review

(3) Per pass clot collection to be sent to Clot Analysis Lab for processing

(4) If more than one NIHSS was performed during this time period, select the worst (highest) value

(5) To be administered pre-procedure by a qualified evaluator; pre-stroke mRS should reflect the subject's condition just prior to the stroke onset. For example, if the subject was hospitalized during stroke onset, the subject's reason for hospitalization should be taken into account when evaluating the subject's pre-stroke mRS

(6) Assessments should be completed for unscheduled visits from the time of Discharge up to (but not including) the 90-day Follow-up, where imaging, NIHSS or mRS is performed as part of stroke management care for the subject

(7) The 90 day mRS must be performed by a qualified independent evaluator. This may be performed by phone per the site's SOC.

(8) AEs will be reported and recorded (via eCRF) if any of the following apply: (a) The event is neurological in nature (b) The event is a serious adverse event (SAE) (c) AE where causality is related to the device or procedure.

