### 3.2.3. Safety Endpoints

1. **Device related serious adverse events within 90 days** –where the EMBOVAC™ Aspiration Catheter caused, or cannot be ruled out as having caused, an event that has resulted in any of the consequences characteristic of an SAE. Device relatedness will be adjudicated by an independent CEC.
2. **Symptomatic Intracerebral Hemorrhage (sICH) at 24 hours specified according to the Heidelberg Bleeding Classification** – adjudicated by an independent CEC - defined as a new intracranial hemorrhage as detected by brain imaging, measured 24 hours after intervention [18], associated with any of the following:
  - $\geq 4$  points total NIHSS at the time of diagnosis compared to immediately before worsening. Note that a 4 points change is not compared with the baseline admission NIHSS score but instead to the immediate pre-deterioration neurological status
  - $\geq 2$  point in one NIHSS category. The rationale for this is to capture new hemorrhages that produce new neurological symptoms, making them clearly symptomatic but not causing worsening in the original stroke territory. For example, a new remote hemorrhage in the contralateral occipital lobe may cause new hemianopia that is clearly symptomatic, but the subject will not have worsening of  $\geq 4$  points on the NIHSS score
  - Leading to intubation/hemicraniectomy/EVD placement or other major medical/surgical intervention
  - Absence of alternative explanation for deterioration
3. **NIHSS at 24 hours post procedure** – NIHSS will be measured at 24 hours and compared to the baseline score.
4. **90 Day All-Cause Mortality** – All mortality regardless of cause at 90 days post-procedure.

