7.1 General Conventions

Descriptive summary statistics will be presented for all endpoints. The number and percentage of subjects will be summarized for categorical variables. Unless specified otherwise, percentages will be based on subjects with non-missing values. Descriptive statistics for continuous variables will include the number of subjects, mean, standard deviation, median, first quartile (Q1), third quartile (Q3), minimum and maximum. All statistical analyses will be performed using SAS® Studio, Version 9.4 or later.

- **Baseline**

Unless specified otherwise, the last non-missing measurement collected during the baseline visit is considered as the baseline measurement (prior to the start of the index procedure).

- The pre-stroke mRS score will be considered as the baseline mRS score.
- The highest (worst) NIHSS score will be considered as the baseline NIHSS score should a subject have more than one non-missing NIHSS score at baseline.

- **Study Day**

Unless specified otherwise, study day will be calculated as the difference between the event/assessment date and index procedure date, i.e., event/assessment date - index procedure date, and the date of index procedure is considered as Day 0.

- Stroke onset date and time

Stroke onset date and time is defined as follows:

- For witnessed stroke, the stroke onset date and time as reported from the case report form (CRF) will be used;
- For un-witnessed stroke, the date and time when the subject was last seen well from CRF will be used.

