7.5.2.2 Secondary Safety Endpoints

Device-related SAEs and all-cause mortality, Kaplan-Meier analysis (using product limit estimates) will be applied. Kaplan-Meier event rate and its associated two-sided 95% CIs using log-log transformation will be reported, the estimate of standard error will be computed using Greenwood's formula.

- **Devices related serious adverse events (SAEs) within 90 days of follow up as determined by an independent Clinical Events Committee**

Kaplan-Meier analysis will be performed to analyze the device related SAE rate within 90 days. Device related SAEs are considered as events; where the event date is the date of first event. Subjects without events will be censored at the date of last contact. The event rate at 90 days with associated 95% CIs will be provided. Device related SAEs beyond 90 days will be listed.

- **sICH at 24h post procedure specified according to the Heidelberg Bleeding Classification (HBC) as determined by an independent Clinical Events Committee**

sICH at 24 hours post procedure as specified by HBC will be assessed. The number and percentage of subjects with events will be summarized with CIs.

- **NIHSS at 24h post procedure**

The observed NIHSS total score at 24 hours post-procedure and changes from the baseline score will be summarized.

- **90 Day All-Cause Mortality**

Kaplan-Meier analysis will be performed to analyze all-cause mortality within 90 days. All-cause mortality is considered as the event; where the event date is the date of mortality. Subjects without events will be censored at the date of last contact. The event rate at 90 days with associated 95% CIs will be provided. Deaths beyond the 90 days will be listed.

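### As the SAP is written, the 24-hour NIHSS change sets the worst baseline score against the most recent 24-hour score, which shifts a safety summary towards improvement; the protocol applies the worst-value rule at both visits, and the two must be reconciled.

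*Protocol*

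**What the plan says.** The endpoint is defined in protocol 3.2.3: "NIHSS will be measured at 24 hours and compared to the baseline score". SAP 7.5.2.2 plans it as a descriptive summary: "The observed NIHSS total score at 24 hours post-procedure and changes from the baseline score will be summarized". SAP 7.13 repeats the change from baseline at the scheduled visits.

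The documents give these rules for choosing among repeated scores:

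- **Protocol Table 1, footnote 4:** "If more than one NIHSS was performed during this time period, select the worst (highest) value". The footnote mark stands on the baseline cell and on the 24-hour cell of the NIHSS row, and on no other cell of that row.
- **SAP 7.1, general baseline rule:** "the last non-missing measurement collected during the baseline visit is considered as the baseline measurement", restricted to values before the index procedure starts.
- **SAP 7.1, exception for NIHSS:** "The highest (worst) NIHSS score will be considered as the baseline NIHSS score should a subject have more than one non-missing NIHSS score" at baseline.
- **SAP section 3 (Interval Windows):** where a measurement is repeated at a visit, the latest non-missing one is used, subject to stated exceptions. The SAP states none for the 24-hour NIHSS.

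The protocol therefore takes worst minus worst, and the SAP takes most recent minus worst.

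**The concern.** The worst of several baseline scores can never be lower than the last one before the procedure. Set against a 24-hour score that is not chosen in the same way, it credits two things to the period after the procedure: any fall in NIHSS before puncture (IV t-PA before the procedure is foreseen in Table 1) and any chance high reading at baseline. Both act in the same direction. A subject who worsened from the last pre-procedure score can then be tabulated as unchanged or improved, in a table meant to describe safety.

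The protocol is careful about the reference score elsewhere. For sICH it measures deterioration from the status just before the worsening and explicitly not from the admission score.

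Because the two documents differ on the 24-hour value, the reported change also depends on which one the programmer follows.

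**Working it through.** **Figures in the plan.** There are none for NIHSS. The only design calculation is the margin for the primary endpoint, 1.96 × √(0.8 × 0.2 / 95) = 0.0804, which matches the stated 8.0% and has no bearing here.

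**Example (invented scores).** Baseline 18, then 12 just before the procedure; 24-hour 20, then 16.

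- Last minus last: 16 − 12 = +4 (worse)
- SAP: 16 − 18 = −2 (improved)
- Protocol: 20 − 18 = +2 (worse)

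If 16 were the only 24-hour score, the SAP and the protocol would both give −2.

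**Average size under the SAP.** The following are assumptions, since the documents supply none of them: two baseline scores, independent and normal with SD s = 2; a mean drift d from the first to the last score; 30 to 50% of subjects with two scores and the rest with one. The shift in a subject with two scores is the expected excess of the worst over the last score:

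E[max − last] = −d × Φ(−d/τ) + τ × φ(d/τ), with τ = s√2 = 2.83.

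For d = −2: 2 × 0.760 + 2.83 × 0.311 = 1.52 + 0.88 = 2.40. For d = +2: −2 × 0.240 + 0.88 = 0.40.

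| Pre-procedure drift d | Shift towards improvement, two scores | Overall, 30% with two | Overall, 50% with two |
|---|---|---|---|
| +2 | 0.40 | 0.12 | 0.20 |
| +1 | 0.70 | 0.21 | 0.35 |
| 0 | 1.13 | 0.34 | 0.56 |
| −1 | 1.70 | 0.51 | 0.85 |
| −2 | 2.40 | 0.72 | 1.20 |

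With no drift, the two-score shift is 0.56, 1.13 and 1.69 points for SD 1, 2 and 3. With three baseline scores and SD 2 it is 1.69.

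**Average size under the protocol (worst at both visits).** Two 24-hour scores of SD 2 raise the 24-hour value by 2/√π = 1.13. With the 24-hour level equal to the last pre-procedure level, the net shift is 1.13 minus the second column of the table (negative means apparent improvement):

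- d = +2: +0.73
- d = 0: 0.00
- d = −1: −0.57
- d = −2: −1.27

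The number of readings matters too. With no drift and SD 2, two baseline scores and one 24-hour score give −1.13, three and two give −0.56, and two and three give +0.56. So the protocol rule has no fixed direction.

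**Masking.** Suppose the true worsening is 4 points, with two readings per visit and no drift. The chance that the recorded change is at least +4 is 0.50 for last minus last and 0.50 for worst minus worst. Under the SAP it is 0.33, because the 24-hour deviation must then be the largest of three exchangeable deviations.

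**Check of the remedy.** Last pre-procedure score against most recent 24-hour score gives a shift of 0.00 at every SD tried. Changing the baseline alone would not do. With a last-value baseline and a worst-value 24-hour score, two 24-hour readings at SD 2 give +1.13, the mirror-image bias.

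**The case against.** Several arguments on the other side have force.

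- **The protocol's rule is symmetric.** A reader who looks only at the baseline rule might infer that improvement is overstated whichever 24-hour value is used. The documents do not support that. Footnote 4 covers both visits, and under it the net shift can be negative, zero or positive. The one-directional shift belongs to the SAP's combination of rules. Under the protocol it needs a fall before the procedure or fewer readings at 24 hours.
- **The SAP tie-break may never operate.** If sites enter only the selected worst score at 24 hours, the protocol rule applies in practice. The documents do not say what the eCRF holds. This limits certainty about the effect but leaves the conflict in the text.
- **The baseline rule is prespecified and the same in both documents.** This is true, and nothing defines the endpoint as change from the last pre-procedure score. The sICH note governs a different, event-triggered definition. A prespecified reference can still be uninformative about what followed the procedure, and the SAP's own default is the better one for that purpose.
- **Worsening is not hidden from the study.** A reader might infer that deteriorating patients disappear from the safety record. They do not: sICH is adjudicated against pre-deterioration status, neurological events are reportable by their nature, and the observed 24-hour score is summarised separately.
- **Repeat baseline scores may be uncommon, and consequences are limited.** The effect is zero with a single score. The study tests no hypothesis, and the NIHSS change has no success threshold or stopping role. This bears on priority and not on whether the rules agree.

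**Conclusion.** The point holds in this form. SAP 7.1 and SAP section 3 together give a 24-hour NIHSS change that is biased towards improvement in every subject whose worst baseline score exceeds the last one before the procedure. They also conflict with footnote 4 on the 24-hour value.

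Under the stated assumptions, the SAP shift is about 0.4 to 2.4 points in subjects with two baseline scores and about 0.1 to 1.2 points in the overall mean. The SD, the drift, the number of readings and the share with repeats are all assumed, so these are indicative ranges and not estimates for this trial.

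The consequence is confined to the descriptive change summaries in SAP 7.5.2.2 and 7.13. It is worth correcting because the change is a named safety endpoint, the bias under the SAP has a known direction, and the correction is cheap.

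**What to change.** 1. In SAP 7.1, restrict the worst-value exception so that it does not apply to the change-from-baseline analyses in 7.5.2.2 and 7.13. For these, use the SAP's own defaults at both ends: the last non-missing NIHSS before the procedure and the most recent 24-hour NIHSS in the window. The 24-hour windows also differ (±12 hours in the protocol, −12 to +48 hours in SAP section 3), so the two must be reconciled before the most recent score is well defined.
2. Reconcile footnote 4 with this by having the eCRF hold both the worst and the last score, at baseline and at 24 hours. If only the worst score is entered, the other change cannot be calculated later.
3. Keep the worst baseline score for the baseline table and for the NIHSS subgroup in SAP 7.12.
4. Report worst minus worst as a sensitivity summary, so that the conservative 24-hour value is not lost.

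The cost is a few lines of SAP and protocol wording, extra eCRF fields, and a source look-up for subjects with repeat scores. The mean change may come out slightly less favourable.
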